The aim of this study is to test whether and to what degree a community-based karate class tailored for individuals with early- to middle-stage Parkinson's Disease (PD) 1) is feasible; and 2) improves objective and patient-reported outcomes. The benefits of exercise for general health and wellbeing in older adults are well-established. Balance exercises such as tai chi and yoga, along with resistance training, can improve or maintain physical function in older adults and enhance muscle strength. Furthermore, aerobic activity is critical for maintaining and improving cardiovascular and functional health. Non-contact boxing has recently seen a surge in popularity among individuals with PD, with components of both aerobic and balance exercise. While participants anecdotally note improvements in stress and physical function, this has only been minimally studied. However, drawing on this experience and the combined aerobic, balance, and mindfulness practices that comprise karate, we hypothesize that participation in structured karate programs may offer similar or greater benefits. In particular, the aerobic, resistance, and balance aspects of karate may be beneficial for physical and cognitive wellbeing, and the mindfulness exercise may improve overall wellbeing. Therefore, we propose a pilot, 10 week-long study of a structured karate exercise program for people with early to middle PD, with pre- and post-intervention assessment of mobility, gait, balance, falls, attention, quality of life, patient-reported global impression of change, and mood. We will assess feasibility with measurement of attendance at each class, and will assess preliminary sustainability with a six-month follow-up phone call to assess continued engagement in karate classes or other regular exercise. We will gather qualitative data on expectations and experience with the classes through pre-intervention and post-intervention focus groups.

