We hypothesize: 1) Subjects will show improved mobility after 10 weeks of twice weekly karate classes, as measured by change in Timed Up & Go (TUG)¹; 2) The majority of subjects will report a positive change from baseline in their overall wellbeing, as measured by a response of "very much improved", "much improved" or "minimally improved" on the Patient Global Impression of Change Scale (PGIC)² following 10 weeks of classes; 3) Feasibility will be high, as measured by $\geq 75\%$ attendance rate and a response of "yes" to either "Would you recommend this program to someone else with PD?" or "If available, would you continue to participate in this or a similar karate class?" Exploratory outcomes will include measures of gait and balance, including change in functional reach test (FRT)³ and change in Tinetti Mobility Test (TMT)^{4,5}, along with change in anxiety and depression, as measured by the Hospital Anxiety and Depression Scale (HADS), and measures of attention such as the Symbol Digit Modalities Test (SDMT) and the Digit Span Test (DST)⁶

I.b. Background

Parkinson's Disease, the second most common neurodegenerative condition⁷ presents a significant health concern and the progressive, incurable course of the disease impacts functional abilities of the patient and quality of life for both the patient and caregivers. Exercise is an established supplement to pharmacologic PD treatment and various modalities have demonstrated benefits in gait, balance, PD symptoms, and quality of life measurements.^{8,9,10} Research has encompassed many forms of exercise, including aerobic activities and mindfulness-based practices. Vigorous, aerobic activity has been repeatedly shown to have disease-modifying effects ranging from quality of life to overall cognitive and physical improvement.¹⁰ Mindfulness-based practices, such as tai chi, have seen a recent surge in interest and an overall beneficial effect for participants.^{11,12} A notable trial compared resistance training,

stretching and tai chi interventions among Parkinson's patients and while both the resistance and tai chi arms showed improvements on multiple measures of physical ability, tai chi demonstrated a significantly greater impact in measures of balance and postural stability.¹³ Furthermore, resistance training and tai chi were both correlated with improved patient-reported outcomes and participants in the tai chi group who reported benefits were more likely to continue their exercise programs.¹⁴

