The PI and research team will collaborate with a professor of Cinema and Television Arts from Columbia College Chicago, IL to develop a documentary to educate others about karate as an interactive form of exercise and its potential benefits on the symptoms and quality of life of people with PD. To capture the groups' journey over 10-weeks, portions of the pre-intervention focus group, the karate classes, and the post-intervention focus group will be videotaped. For a more in-depth look, two to three subjects will be followed during the entire study and interviewed to provide a personal narrative of their experiences with the karate classes and living with PD. The interviews will be videotaped.

We will recruit 30 individuals with PD diagnosed by a neurologist, ages 30-90, living in Chicago, and with Hoehn & Yahr (HY) stage 1 (unilateral symptoms, no balance issues), stage 2 (bilateral symptoms, no balance issues), or stage 3 (bilateral symptoms, some postural or balance involvement). Subjects will be assigned to one of two cohorts of 15 subjects each, based on dojo location and class schedule. For example, one cohort may take classes Tuesday and Thursday nights at the Wilmette dojo, and the second cohort may take classes Wednesday and Saturday mornings at the Glenview dojo, however class times and locations are to be determined.

II. Characteristics of the Research Population

II.a. Number of Subjects

Total Number of Subjects: 30

This is a pilot study; our power analysis (see table below) is based on the TUG, with the following assumptions: mean TUG score for individuals with PD is 14.8 seconds with standard deviation of 5.8 seconds, alpha of 0.05, and correlation between baseline and follow-up assessments of 0.5. We calculated sample sizes necessary with various minimum clinically important difference values for the TUG, which ranges from 2 seconds to 5 seconds in various studies^{1,18}, and varying for power between 80-90%. With a sample size of 30, we will have 80% power to detect a change of 3 seconds in the TUG, and will be more than 90% powered to detect a change of 4 seconds or greater.

| Baseline mean TUG | Baseline SD TUG | Min. clin. Important difference | Correlation b/w baseline, follow-up | Power | Sample size |
|-------------------|-----------------|---------------------------------|-------------------------------------|-----------|-------------|
| 14.8s | 5.8 | 2s | 0.5 | .9 | 89 |
| | | | 0.5 | .8 | 67 |

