Oversight of the Data: Karate for PD will be maintained by the Principal Investigator. The Principal Investigator will review study procedures annually and report any concerns in the IRB continuation application. This is a Level I, Low, Minimal Risk study; therefore, there is minimal risk of unanticipated problems with the exception of breaches in confidentiality. The quantitative data for the study will be entered into a secured database using an electronic data capture program, Research Electronic Data Capture (REDCap).²² The database will be stored on a secure password-protected server and not on individual desktop computers. The code sheet will be password protected and the password will be updated annually. Breaches of confidentiality will be reported to the IRB immediately with the “Reportable Event/Unanticipated Problem Form.”

Data will be exported from REDCap in de-identified format for statistical analysis, with all PHI stripped from the dataset prior to analysis by statisticians. We will summarize categorical variables by

frequencies and percentages and will assess continuous variables for normality, summarized by mean/standard deviation, or median/interquartile range. We will report the basic descriptive statistics of the cohort, including baseline TUG, FRT, TMT, HADS, PDQ-8, SDMT, and DST, stratified by HY stage. We will report on attendance, defined as the percentage of classes attended, where 20 is the denominator. We will analyze the change in TUG, FRT, TMT, HADS, PDQ-8, SDMT, and DST, respectively, from pre- to post-intervention, using paired *t*-tests or nonparametric Wilcoxon sign rank tests, as appropriate, stratifying for HY stage. We will report on the percentage of subjects endorsing each of the 7 PGIC response options, stratifying for HY stage. We will report the descriptive statistics concerning whether subjects' individual predefined goal for the class was achieved (binary outcome), and will present de-identified qualitative comments noted in the feedback at the post-intervention assessment. We will report descriptive statistics on continued interest and likelihood of recommending the program to someone else with PD. After the 6-month follow-up call, we will analyze descriptive statistics on continued involvement in karate/martial arts, and will again report the percentage of subjects endorsing each PGIC response option.

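### TUG drives the power analysis but is never named primary, PDQ-8 is tested without a rank, and III.b does not specify the whole-sample TUG test or the status of HY-stage results

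*Combined protocol and SAP*

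**What the plan says.** The second aim is to test whether karate "improves objective and patient-reported outcomes"; it names no single measure.

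The hypotheses paragraph, just before I.b, gives three hypotheses:

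- Hypothesis 1: "Subjects will show improved mobility after 10 weeks of twice weekly karate classes, as measured by change in Timed Up & Go (TUG").
- Hypothesis 2: "The majority of subjects will report a positive change from baseline in their overall wellbeing", measured by the PGIC.
- Hypothesis 3: "Feasibility will be high, as measured by" attendance of at least 75% and a yes to either of two questions.

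It then sets other measures apart: "Exploratory outcomes will include measures of gait and balance, including change in functional reach test (FRT") and the TMT, "along with change in anxiety and depression, as measured by the Hospital Anxiety and Depression Scale (HADS), and measures of attention", namely the SDMT and DST. PDQ-8 is in no hypothesis and is not in this list.

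In II.a, "our power analysis (see table below) is based on the TUG", with SD 5.8 s, correlation 0.5 and alpha 0.05. It gives 30 subjects for 80% power to detect 3 s.

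In III.b, "We will analyze the change in TUG, FRT, TMT, HADS, PDQ-8, SDMT, and DST, respectively, from pre- to post-intervention, using paired" t-tests or Wilcoxon tests, stratified by HY stage. The section states no lead outcome, no exploratory label, no significance threshold and no multiplicity rule. It does not say whether a pooled test will be run or what a result in one stage would count for. PGIC and the two feasibility questions are only to be described.

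**The concern.** The design section has an implied order (TUG first, five measures exploratory), and the analysis section does not reproduce it. Three things are left open.

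1. The test that II.a powers, one TUG comparison in all 30 subjects, is not specified in III.b. The only TUG analysis described there is stratified.
2. PDQ-8 is the only quality-of-life scale. It is patient-reported, so it fits the second aim as worded, yet it has no rank.
3. HY-stage results carry no exploratory label anywhere, even for TUG.

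Suppose TUG shows no change overall, but PDQ-8 or TUG in one stage reaches p<0.05. The plan does not say whether that supports the second aim. The stated alpha and power describe a single pooled TUG test, so they do not carry over to a conclusion reached by another route.

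**Working it through.** **Inputs from the documents.** SD 5.8 s, correlation 0.5, alpha 0.05, N = 30, change of 3 s (II.a); seven change scores (III.b); HY stages 1, 2 and 3 (I.c).

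**Assumed.** Two-sided tests, correlation between change scores of 0 to 0.8, and HY-stage sizes. III.b gives no threshold, so 0.05 is taken from II.a.

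**Step 1: reproduce the plan's sample size.** SD of change = 5.8 × √(2 × (1 − 0.5)) = 5.8 s. With n = [5.8 × (1.96 + z_power) / difference]², rounded up:

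| Difference | 90% power | 80% power |
|---|---|---|
| 2 s | 89 | 67 |
| 3 s | 40 | 30 |
| 4 s | 23 | 17 |
| 5 s | 15 | 11 |

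All eight entries match the table. A one-sided test would give 24 for the 3 s, 80% entry, which does not match. So the plan's alpha and power describe one two-sided TUG test in the whole sample. Power for 3 s at N = 30 is 80.9% by this formula and 78.2% by the exact paired t-test.

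**Step 2: honour the exploratory label.** Of the seven tested outcomes, only TUG and PDQ-8 are not called exploratory. If they are independent and nothing changes, the chance of at least one p<0.05 is 1 − 0.95² = 9.75%. In simulated null trials with 30 subjects it is about 9% at correlation 0.5 and 8% at 0.8. Counting only improvement, it is 1 − 0.975² = 4.9% if independent and about 5% at correlation 0.5, against 2.5% for a single test.

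**Step 3: read stratifying as separate tests in three stages.** This is the upper reading.

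- TUG alone: 1 − 0.95³ = 14.3%.
- TUG and PDQ-8, independent: 1 − 0.95⁶ = 26.5%. In simulation with 10 subjects per stage, about 25% at correlation 0.5 and 22% at 0.8.
- Counting only improvement, TUG and PDQ-8 give about 13% at correlation 0.5.

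**Step 4: power within a stage.** Exact paired t-test, 3 s, SD of change 5.8 s:

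| Subjects | Power |
|---|---|
| 8 | 24% |
| 10 | 31% |
| 14 | 43% |
| 30 (pooled) | 78% |

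**Step 5: the remedy compared with an alpha split.** Naming one pooled TUG test keeps 5% error for Hypothesis 1 and N = 30. Treating all seven outcomes as equal routes with Bonferroni (0.05/7 = 0.00714) would cut TUG power for 3 s to 55.7% (normal formula) or 48.7% (exact t), and 80% power would need 47 subjects.

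**The case against.** The strongest reply is that the ranking is already largely there. TUG is Hypothesis 1 and the only outcome powered, and five of the seven tested outcomes are called exploratory. In a single combined document, III.b need not repeat that label for it to apply. Hypotheses 1 and 2 also map onto the objective and patient-reported halves of the second aim. This stands. A reader might infer that any one of the seven tests, in any stage, could establish the second aim. The corresponding false-positive chances are about 23% pooled (15-30% over correlations 0 to 0.8) and about 57% by stage (41-66%, assumed stages of 8, 14 and 8). The documents do not support that inference: a claim resting on FRT, TMT, HADS, SDMT or DST would contradict the protocol's own label.

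The exploratory list is also worded as open, so PDQ-8 may be meant to belong to it. That is plausible, but it is not written.

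Stratifying may mean no more than reporting by stage; III.b uses the same term for descriptive PGIC percentages. So the by-stage figures are an upper reading. The ambiguity remains, because no pooled TUG test is written down.

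Finally, this is an uncontrolled, open-label pilot, so even a significant TUG change could not be attributed to karate. That limits the practical weight of the error rates. But the protocol chose hypothesis tests and a power calculation, and one sentence would tie the two together.

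**Conclusion.** The point holds in a narrow form. TUG is the de facto lead outcome but is not named primary, PDQ-8 has no rank, and III.b specifies neither the pooled TUG test nor the status of stage results.

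On the reading most favourable to the plan (pooled tests, label honoured), the chance of a nominal finding rises from 5% to about 9%. On the upper reading it is about 14% for TUG alone and 25% for TUG and PDQ-8, with about 31% power in a stage of 10. These figures rest on assumed two-sided 0.05 tests, assumed correlations and assumed stage sizes.

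A reader might also infer that TUG alone should decide the second aim. The documents do not support that either: Hypothesis 2 gives the patient-reported half its own measure, and the three hypotheses are not ranked against each other. Some pages of the protocol were not available for review, so a primary label there cannot be excluded; the available hypotheses, sample-size and analysis text contains none.

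This should be changed because it affects what may be concluded and costs almost nothing.

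**What to change.** - In III.b, state that the paired test of TUG change in all subjects with both assessments, two-sided 0.05, is the primary test of Hypothesis 1.
- In the hypotheses paragraph, add PDQ-8 to the exploratory outcomes.
- In III.b, label FRT, TMT, HADS, PDQ-8, SDMT, DST and all HY-stage results exploratory, reported as change with 95% confidence intervals.
- Keep Hypothesis 2 (PGIC) and Hypothesis 3 (feasibility) as separate hypotheses, reported as planned and not subordinate to TUG.

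The cost is a few sentences. N stays at 30, no data are added and every planned analysis is kept. The small downside is that a nominally significant PDQ-8 or single-stage result could be presented only as exploratory.

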This is a non-randomized, open-label, non-blinded, 10-week pilot study of a novel intervention, namely, non-contact karate, for early to middle stage PD. The intervention—namely, karate classes—are developed for and will include only patients with Parkinson's disease. Eligible subjects will engage in twice-weekly karate classes for 10 weeks, specifically designed for individuals with early to middle stage PD, focused on incorporating upper and lower limb movements in multiple directions, increasing awareness throughout the body, shifting body weight and rotation, relaxation of the muscles, improving reaction time, using complex repetitive actions to improve coordination, footwork training and centered weight shifts to help with fall prevention, and striking shields for self-defense and stress relief.

Each subject will attend a pre-intervention focus group, at which time the study logistics will be reviewed, informed consent process will occur, the subject will complete a brief, individual pre-intervention assessment focused on overall mobility, gait, balance, attention, mood, and quality of life, and the subjects will be prompted to share aloud their thoughts on exercise, balance, and mindfulness practices in general and in PD specifically, and any expectations or preconceptions that they have regarding karate classes for PD. The focus group sessions will be audiotaped. After the sessions the information recorded will be transcribed into electronic documentation for later review and analysis. At the end of the study, the audiotapes will be destroyed.

Following 10 weeks of twice weekly classes, the subjects will have a post-intervention assessment and focus group, in which the pre-intervention assessments (TUG, FRT, TMT, PDQ-8, HADS, SDMT, DST) will be re-administered, along with the PGIC for the subject's global impression of change. Subjects will be prompted to share their thoughts on how the intervention impacted their overall wellbeing, balance, and mindfulness; whether the intervention achieved their expectations; and they will be asked to provide feedback for improvements. Finally, the study team will contact subjects 6 months post-intervention to assess continued engagement in karate or related activities and again, the subject's quality of life and global impression of change.

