| 14.8 | 5.8 | 3s | 0.5 | .9 | 40 |
| | | | 0.5 | .8 | 30 |

| | | | | | |
|------|-----|----|-----|----|----|
| 14.8 | 5.8 | 4s | 0.5 | .9 | 23 |
| | | | 0.5 | .8 | 17 |
| 14.8 | 5.8 | 5s | 0.5 | .9 | 15 |
| | | | 0.5 | .8 | 11 |

II.b. Gender of Subjects

There will be no exclusion of subjects based on gender.

II.c. Age of Subjects

Subjects will be 30-90 years of age.

II.d. Racial and Ethnic Origin

There will be no exclusion of subjects based on racial or ethnic characteristics. However, subjects must be fluent in English to participate in the karate classes, as that is the language of instruction, and due to the general lack of appropriately translated neurological and neuropsychological assessments and appropriate normative comparison samples. These factors are critical for accurate administration, scoring, and interpretation of neurological and neuropsychological test data.

II.e. Inclusion Criteria for All Subjects:

1. Each subject must be between 30-90 years of age. A subject may be of either gender, any race/ethnicity.
2. Subjects will be those diagnosed with Parkinson's Disease by a treating neurologist; if the subject is seen at Rush University Medical Center, this will be verified via chart review. If the subject is seen elsewhere, he or she will be asked to have their neurologist sign a form confirming the diagnosis of Parkinson's Disease and indicating the subject's HY stage (with definitions of each stage provided on the form for providers who may not be familiar with HY staging) at the most recent visit, to be sent back to the study coordinator for eligibility verification.
3. English speaking.
4. Living within the Chicago area.
5. Subjects may be untreated for Parkinson's Disease, or may be taking any individual PD medication or combination thereof. Subjects may or may not have had Deep Brain Stimulation. Subjects may or may not be receiving physical or occupational therapy. Subjects will be encouraged to maintain their same medication regimen throughout the duration of the 10-week study, however if emergent issues arise requiring medication changes, the subject will not be disqualified.

II.f. Exclusion Criteria for All Subjects

1. Subjects requiring an assistive device (cane, walker, wheelchair) or the assistance of another person in order to ambulate.
2. Subjects with active psychosis or exhibiting symptoms of a severe psychiatric disorder.

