There are no known risks from participating in neurological or neuropsychological tests. Subjects may experience mild boredom or cognitive fatigue; however, most individuals with like symptoms find the tests interesting and are able to tolerate up to two-hour duration of testing well. There is, however, a risk of falls or injury associated with participation in any exercise, including karate, for which subjects will sign a liability waiver used for all karate class participants at the Fonseca Martial Arts dojos. The risks will be minimized to the extent possible by 1) having all instructors undergo basic instruction in principles of PD by the PI prior to the first class; 2) having all classes held at quieter times in the dojo, so as to avoid overcrowding and risks of falls or freezing of gait in crowded, busy situations; 3) having small instructor to subject ratios (2 instructors per 15 subjects) to allow for maximal supervision and guidance; 4) having study staff present to assist with mobility issues at as many classes as possible.

Another possible risk is the loss of confidentiality by participating in the video because the subject's image may be captured. However full names will not be used during interviews with the two or three subjects who agree to answer questions about their experiences with the karate classes.

IV.b. Potential Benefit to Subjects

Potential benefits to subjects include the following: 1) cognitive and physical improvements in PD symptoms related to both vigorous physical activity and mindful exercise; 2) benefits of mindful exercise on quality of life; 3) the enjoyment of participating in a new activity in a social environment with other individuals with PD; 3) the satisfaction of learning a new skill; 4) the knowledge that by participating,

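### No visible eligibility criterion or described clinician check covers a known general-medical reason not to do the class in a person who walks unaided and has no severe psychiatric disorder

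*Combined protocol and SAP*

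**What the plan says.** **Who may enter.** II.e item 1 reads "Each subject must be between 30-90 years of age". Section I.c limits disease stage to HY 1, 2 or 3, the last being "stage 3 (bilateral symptoms, some postural or balance involvement". The remaining inclusion criteria concern the PD diagnosis, English, residence, and a permissive clause on PD treatment.

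**Who may not.** II.f item 1 excludes "Subjects requiring an assistive device (cane, walker, wheelchair) or the assistance of another person in order to ambulate". Item 2 excludes active psychosis or severe psychiatric disorder. Items 3 to 5 concern ability to attend, recent martial arts or boxing, and atypical parkinsonism.

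**What clinicians are asked.** Under II.e item 2, a patient seen elsewhere has the neurologist "sign a form confirming the diagnosis of Parkinson's Disease and indicating the subject's HY stage". For a study-centre patient the diagnosis is the item checked: "this will be verified via chart review".

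**The exposure and its risk.** Section I.c states "Eligible subjects will engage in twice-weekly karate classes for 10 weeks, specifically designed for individuals with early to middle stage PD". Section I.b describes karate as vigorous aerobic and resistance activity, and IV.b lists among the hoped-for benefits "cognitive and physical improvements in PD symptoms related to both vigorous physical activity and mindful exercise". IV.a acknowledges "a risk of falls or injury associated with participation in any exercise, including karate, for which subjects will sign a liability waiver". It then names four precautions: PD training for instructors, quieter class times, two instructors for 15 participants, and study staff at as many classes as can be covered. III.b classes the study as minimal risk, and I.c describes the karate as non-contact.

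**The concern.** A person whose own clinician knows of a somatic reason not to do this class could meet every visible criterion, provided that he or she walks without help and has no severe psychiatric disorder. Candidates respond to recruitment material and telephone the coordinator, and the call screens for eligibility and availability. It can apply only the criteria that exist.

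What is at stake is participant safety. Supervision in class and review of adverse events come into play once the person is exercising. A question before the first class acts on entry.

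**Working it through.** No calculation in the plan bears on this point, so the check sets the entry steps side by side and asks of each whether it would stop such a person.

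1. **Criteria (II.e and II.f).** 5 + 5 = 10 listed criteria.
   - Two are partial safety filters: exclusion 1 (walking aid or helper needed) and exclusion 2 (psychosis or severe psychiatric disorder). Exclusion 1 applies whatever the cause, so it also catches non-PD conditions severe enough to require a walking aid.
   - The other 10 − 2 = 8 are age, PD diagnosis, language, residence, permitted treatment, ability to attend, recent martial arts, and atypical parkinsonism. None is a general-medical exclusion, a contraindication clause or an investigator-judgement clause.

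2. **HY limit (I.c).** This restricts PD severity. It says nothing about the heart, bones or recent surgery.

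3. **Clinician input (II.e item 2).** The outside form is described with two contents (diagnosis and HY stage), and the chart review with one (diagnosis). Neither is described as asking about fitness for the class.

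4. **Screening call (III).** Described as covering eligibility and ability to attend the scheduled classes.

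5. **Baseline visit (III).** The questionnaire has 10 fields (name, phone, age, gender, race, ethnicity, PD duration, prior martial arts, activity level, falls) plus 1 open question, 11 in all. Activity level and falls bear most directly on exercise safety. Both are collected after consent, and the text ties neither to entry. The motor examination at the same visit serves to determine HY stage.

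6. **IV.a precautions and III.b monitoring.** The four precautions govern how classes run. The waiver is described as dealing with liability, not as a medical check. Adverse events are reviewed as they occur, which is after exposure.

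No described step asks a clinician whether there is a known medical reason not to do the class. The counts show how far the visible text goes. They involve some judgement (age or PD duration could also be thought relevant to safety), and they do not measure harm.

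**The case against.** **Unseen text.** Part of section V, the consent form, the neurologist form and the waiver were not available for this review. Exclusion 5 mentions a referring neurologist, although no visible section describes a referral step. A reader might infer that the trial has no medical check anywhere. The documents do not support that, because a procedural check could sit in the unseen text. What stands is narrower: the two criteria lists are visible, and they contain no such criterion.

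**Low risk.** The study is classed as minimal risk, the karate is non-contact, classes last 45-60 minutes and build up over ten weeks, and much of Appendix 1 is gentle. The IV.a precautions are a real risk plan. A reader might infer that safety has been neglected or that injuries are to be expected. Neither follows: two exclusions and four precautions are in place, and no event rate is given. Yet Appendix 1 also includes one-leg squats and kicks, and the precautions work inside the class.

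**Design choice.** A community exercise pilot may reasonably rely on self-selection and a waiver. A neurologist may not know every non-neurological reason, and a question without a threshold will be answered differently by different clinicians. All of this is fair. It argues for keeping the remedy light. The form already goes to a clinician, so one further question adds little burden.

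**Conclusion.** The point holds as a minor safety improvement. On the visible text, a person with a known somatic contraindication who walks unaided and has no severe psychiatric disorder would pass every listed criterion and every described clinician check.

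The size of any harm cannot be stated, because the documents give neither the prevalence of such conditions nor an expected rate of falls or injuries. A reader might infer that the results would be biased. They would not be on this account: no planned analysis is affected, and stopping for physical reasons is genuine feasibility information that should be counted.

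The conclusion assumes that the form and chart review contain no more than II.e describes, and that the unseen section V and consent text contain no equivalent check. If the second assumption fails, what remains is that II.f does not reflect the check.

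**What to change.** Before the first class:

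- Add to II.f an exclusion for anyone whose treating clinician, or the PI, knows of a medical reason not to do the described class. Set no fixed clinical threshold.
- Add one yes/no line on this to the existing outside neurologist form, and attach Appendix 1 so that the clinician can see what the class involves.
- For study-centre patients, have the treating neurologist or the PI answer the same question alongside the chart review.

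If section V or the consent form already has such a check, only align II.f with it.

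The cost is one sentence in II.f, one line on a form already in use, and one answer per candidate: 1 × 30 = 30 for the enrolled sample, plus any candidates who do not enrol. No extra visit or test is needed. The downsides are that a few interested people may be excluded and that a neurologist will not know every non-neurological reason, so the question narrows the gap without closing it.
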